6.4 STUDY INTERVENTION/EXPERIMENTAL MANIPULATION ADHERENCE

The Summer Camp setting is designed to maximize attendance for intervention sessions. Attendance is facilitated by stating the fixed dates of the study in advance (including on recruitment materials), by providing a detailed week-by-week camp schedule before the start of camp, and by daily contact with families during drop-off and pick-up. Absences will be logged daily during camp weeks to enable adjustment for amount of intervention received.

During intervention sessions, adherence to protocol may be reduced due to frustration experienced by the child during difficult treatment tasks. SLPs provide a supportive environment, clear structure with visual supports, and breaks with engaging fun activities to manage the child's behavior and motivation to continue to engage. Tracking sheets are completed each session to log the number of teaching episodes completed, and which targets and utterances are practiced how many times. All sessions are audio- and video-recorded for off-line review. Parents must agree to have their child recorded for data analysis and verification purposes in order to participate (additional uses of recordings are optional).

6.5 CONCOMITANT THERAPY

No restrictions are placed on participating in this study. Children are allowed to continue with any regular or additional speech therapy services they receive elsewhere (usual care). We ask parents to disclose any concomitant speech therapy prior to the start of camp as well as after T3 data collection. Any details about concomitant therapy (received, amount, type) is documented in the participant data file. Concomitant speech therapy is unlikely given the intensity and full-day commitment (8:00 am – 3:00 pm, 4 days/week for 4 weeks).

6.5.1 RESCUE THERAPY

N/A

7 STUDY INTERVENTION/EXPERIMENTAL MANIPULATION DISCONTINUATION AND PARTICIPANT DISCONTINUATION/WITHDRAWAL

7.1 DISCONTINUATION OF STUDY INTERVENTION/EXPERIMENTAL MANIPULATION

We do not anticipate serious adverse events from the intervention. However, we monitor child frustration during treatment sessions throughout the trial, as described below.

Treating speech-language pathology (SLP) graduate students note in daily treatment progress notes the degree of each child's frustration level on a 4-point scale involving the SLP's judgment based on behavior observed during the session (e.g., crying, refusal to speak). In this scale, 0 = no frustration, full

compliance with procedures throughout session; 1 = some frustration, occasional non-compliance with procedures during session; 2 = significant frustration, frequent non-compliance with procedures during session; 3 = marked frustration, non-compliance during entire session).

SLPs discuss with the PI, Co-I [name], and the SLP supervisors at the end of each treatment day those children who are judged to experience significant or marked frustration (scores of 2 and 3) in a session. On a daily basis during Summer Camp, this team discusses possible strategies to minimize or eliminate the child's frustration in subsequent sessions. For children who experience recurrent significant or marked frustration (scores of 2 or 3 across more than three consecutive treatment days), the PI and Co-I [name] will discuss with parents the options of continuing or withdrawing from the study. The PI is responsible for reporting withdrawals to the IRB.

7.2 PARTICIPANT DISCONTINUATION/WITHDRAWAL FROM THE STUDY

7.2.1 INDIVIDUAL PARTICIPANT DISCONTINUATION/WITHDRAWAL

Participants are free to withdraw from the study at any time and for any reason without consequence by contacting the Investigator or appropriate research personnel. Data to be collected on discontinuation of ASSIST will include the reason(s) for discontinuation. When a child discontinues from the ASSIST intervention but not from the study, remaining study procedures will be completed as indicated by the study protocol. Withdrawal from this study does not preclude children from participating in future studies in the SLAB Lab or any other lab at Temple University, nor does it jeopardize any other relationship with Temple University they may have now or in the future (including clinical services through the TU Speech-Language-Hearing Center). Parents and children are informed during the consent process of their right to withdraw at any time.

We do not anticipate withdrawing participants without their consent. However, participants may be withdrawn from the study:

- If they develop a medical condition that makes it difficult to continue or may be contagious.
- If they meet an exclusion criterion (either newly developed or not previously recognized) that precludes further study participation.
- If they repeatedly fail to follow study procedures or experimenter directions which would make it impossible to obtain usable data (e.g., repeatedly refusing to follow the clinician's directions).
- If they repeatedly fail to show up for scheduled appointments. Repeated cancellations may result in data that is incomplete or difficult to interpret. Such situations would be wasteful of valuable resources, and participants may be withdrawn from the study without their consent. If this occurs, the PI or appropriate research personnel will make a reasonable attempt to explain the reason for withdrawal. We expect that participants will attend their scheduled appointments and will contact us if they need to reschedule.

The reason for participant discontinuation or withdrawal from the study will be recorded on the ASSIST Case Report Form (CRF). Children who are randomized will not be replaced regardless of whether they have received any intervention.

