4.1.2.2 INTERVENTION

All children receive 16 hours (32 sessions of 30 minutes) of ASSIST, across 4 sessions per day, 4 days per week for 2 weeks (either the first two weeks or the second two weeks). All children are tested 1 week before treatment (T1), after 2 weeks (T2), and post treatment (T3). The critical comparison is at T2 for Study 1 (ASSIST vs. No ASSIST), at T3 for Study 4 (Massed vs. Distributed ASSIST), and post treatment (T2 or T3) for Studies 2 and 3 (Simple vs. Complex and Word vs. Nonword ASSIST).

ASSIST (Apraxia of Speech Systematic Integral Stimulation Treatment) is a theoretically grounded and clinically informed speech therapy intervention for CAS. ASSIST involves repeated structured practice of meaningful words and phrases with cueing and feedback. It incorporates principles of motor learning and systematically adapts difficulty and introduces new targets based on a child's performance. Targets are embedded in carrier phrases (frames).

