5.5.2 RETENTION STRATEGIES

Given the near-daily contact during camp weeks, visit reminders are generally unnecessary but are sent if requested or necessary. For assessment visits, parents receive e-mail or phone reminders within a few days of the appointment.

The following strategies are implemented to retain children for the duration of each study:

- (1) We explain the importance of completing the study to the parents before enrolling so that they can make a decision whether they wish to enroll their child. If a parent decides to withdraw their child after enrollment, we will ask if they are nevertheless willing to return for post-testing to minimize data loss.
- (2) We offer the treatment at no cost to parents (nor is insurance involved). This provides an incentive for all parents, and reduces the risk of differential attrition by socio-economic status.
- (3) We offer the treatment in a relatively short period of time (7 weeks in summer, plus evaluation prior to treatment). This reduces the risk of life events impacting attrition (e.g., moving away).
- (4) We offer the treatment as a Summer Camp experience, where parents drop off their children in the morning and pick them up in the afternoon at fixed times. This facilitates scheduling and forming a routine, and allows parents to conduct their normal affairs during the day. We provide snacks for the children but ask parents to pack a lunch for their children.
- (5) We strive to make the Summer Camp fun for the children. Each day has a variety of group activities, conducted by trained camp counselors (supervised by a camp leader) who have experience working with children. Children may do arts and crafts and take their projects home. Children may also earn small prizes as rewards during their treatment sessions.
- (6) We offer to share copies of evaluation reports with the parents, as well as copies of treatment progress and resulting publications (after completion of the study).

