9.4.3 ANALYSIS OF THE SECONDARY ENDPOINT(S)

Analysis of secondary endpoints (see **Section 9.1, Statistical Hypotheses**) is not dependent on findings for the primary endpoint. Analysis of secondary endpoints is as described above for the primary endpoint (**Section 9.4.2, Analysis of the Primary Endpoint(s)**).

For Secondary Endpoint 1 (perceptual accuracy of full 30-item target set), perceptual accuracy analysis procedures are as described above for the primary endpoint. For Secondary Endpoint 2 (ICS) and Secondary Endpoint 3 (FOCUS), we use mean score across items. For Secondary Endpoint 4 (TOCS+), we use the mean percentage accuracy across listeners. Variables entered into analyses are change scores computed based on the same timepoints as for the primary endpoint as described above (**Section 9.4.2, Analysis of the Primary Endpoint(s)**). No imputation will be used for any missing data.

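### Children withdrawn from the study by the team have no stated T2/T3 follow-up, and before T2 the treatment-session triggers arise only in the Immediate arm, so losses in Study 1 can be differential

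*Protocol*

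**What the plan says.** Protocol Section 7.2.1 lists grounds on which the team may withdraw a randomised child from the study. Three matter here:

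- Eligibility found wanting after randomisation: "If they meet an exclusion criterion (either newly developed or not previously recognized) that precludes further study participation"
- Non-compliance, where refusal of the treating clinician's directions is the example given: "If they repeatedly fail to follow study procedures or experimenter directions which would make it impossible to obtain usable data"
- Poor attendance in either arm: "If they repeatedly fail to show up for scheduled appointments"

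Section 7.1 adds a frustration trigger, "scores of 2 or 3 across more than three consecutive treatment days", after which continuing or withdrawing is discussed with the parents.

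Two provisions protect outcome data. Section 7.2.1 keeps the remaining assessments for a child who stops ASSIST but stays in the study. Section 5.5.2 covers a parent's decision: "If a parent decides to withdraw their child after enrollment, we will ask if they are nevertheless willing to return for post-testing". Neither mentions a child whom the team withdraws from the study.

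On analysis, Section 9.4.2 compares T2 minus T1 change between arms. Section 9.4.3 states: "No imputation will be used for any missing data". Section 9.3 uses a modified intention-to-treat set that requires at least one ASSIST session. The SAP does not address missing data or withdrawals.

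**The concern.** Study 1 compares the arms at T2. Children receive ASSIST in "either the first two weeks or the second two weeks" of camp, so the Immediate arm is treated before T2 and the Delayed arm after it. Two triggers depend on treatment sessions: refusing the clinician's directions, and recurrent frustration, which the protocol's scale defines largely by non-compliance. Before T2 both can occur only in the Immediate arm. That arm also has up to 32 individual sessions with clinicians and supervisors before T2, so a speech-related exclusion such as dysarthria is more likely to be noticed there.

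An Immediate child withdrawn by the team after a first session stays nominally in the modified intention-to-treat set. Without a T2 score, however, the child has no change score and drops out of the t-test. If such children tend to gain less, the treated arm keeps its better gainers. The estimated effect is then too large, in a trial meant to supply effect sizes for later phases.

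**Working it through.** **Who is exposed to what before T2 (Study 1)**

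| Ground | Immediate | Delayed |
|---|---|---|
| Refusing the treating clinician's directions (7.2.1) | yes | no, ASSIST not yet started |
| Recurrent frustration in sessions (7.1) | yes | no |
| Refusing other study procedures, e.g. testing (7.2.1) | yes | yes, at T1 and T2 |
| Exclusion criterion newly recognised (7.2.1) | yes, with closer observation of speech | yes, in camp and at testing |
| Missed appointments (7.2.1) | yes | yes |

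**The plan's own figure.** Inputs from Section 9.2: 20 per arm, effect size 0.909, two-sided alpha 0.05. Power is taken from the noncentral t distribution with n1 + n2 − 2 degrees of freedom and noncentrality d / √(1/n1 + 1/n2). For 20 and 20 it is 79.99%, which reproduces the stated 80%. The other rows of Table 2 reproduce to within about one point.

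**Power after random loss from one arm.** With 18 and 20, power is 77.7%; with 16 and 20, it is 75.0%. Power is therefore not the main issue.

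**Bias after selective loss.** The documents give neither withdrawals by arm nor a link between compliance and gain, so both are assumed. The model has change scores with SD 1 in both arms and no true effect. Compliance is correlated r with gain, the k least compliant of 20 Immediate children are lost, and no Delayed children are lost. Then

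bias = r × S(k) / (20 − k),

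where S(k) is the sum of the k largest expected normal order statistics for n = 20 (1.8675, 1.4076, 1.1309, 0.9210).

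- k = 2: S = 3.2751; 3.2751 / 18 = 0.182
- k = 4: S = 5.3270; 5.3270 / 16 = 0.333

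The last two columns come from simulation (200,000 replicates) and give rejections in favour of ASSIST, nominally 2.5%.

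| r | Bias, 2 lost | Bias, 4 lost | False positive, 2 lost | False positive, 4 lost |
|---|---|---|---|---|
| 0.3 | 0.05 SD | 0.10 SD | 3.7% | 4.8% |
| 0.5 | 0.09 SD | 0.17 SD | 4.8% | 7.3% |
| 0.7 | 0.13 SD | 0.23 SD | 6.1% | 11.1% |

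(At r = 0.5 with 4 lost, the formula gives 0.1665 and simulation 0.165.)

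**Effect of Delayed losses.** The same formula with k = 1 gives 1.8675 / 19 = 0.098. With 2 Immediate and 1 Delayed lost at r = 0.5, bias is 0.5 × (0.182 − 0.098) = 0.04 SD. With 2 lost from each arm it cancels.

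**The case against.** A reader might infer that only the Immediate arm is exposed to the withdrawal rules before T2, or that the control arm is left untouched. The documents do not support either. The exclusion, attendance and study-procedure rules are neutral between arms. Delayed children attend the same camp (Section 6.1.1.1.4), are tested at T1 and T2 under live supervision (10.1.8), and can be found to meet criteria such as toileting or separation (5.2). Most exclusion criteria rest on referral diagnosis or parent report; only oral structure and dysarthria are the clinician's judgement, and both are examined at length at screening. As Section 9.3 is written, a Delayed child lost before week 5 also leaves the analysis set, because that child has had no ASSIST session.

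The rules also carry limits. Refusal counts only if usable data become impossible to obtain, and an exclusion criterion only if it precludes participation. The protocol does not expect to withdraw children without consent and expects few withdrawals of any kind (7.2.1, 7.2.2). The frustration route goes through the parents, and a parent's decision brings the post-testing request in 5.5.2.

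The size rests on assumption. No document links non-compliance to gain. In a model with no treatment effect, missed treatment cannot create that link, so it would have to come from the child's other characteristics. The tolerance in Section 7.2.2 of fewer than 5 losses per 20 children a year covers all causes and both arms and concerns power, so it does not support any particular number of team-led withdrawals from the Immediate arm.

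All of this stands, and it narrows the point. It does not fill the gap: no T2 or T3 follow-up is stated after team-initiated withdrawal, and the session-based triggers are unequal before T2.

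**Conclusion.** The point holds as a risk of differential loss, not as a demonstrated one-sided exclusion. Under the stated assumptions the bias is 0.05 to 0.13 SD for 2 Immediate losses and 0.10 to 0.23 SD for 4, against a design effect of 0.909 SD. These figures assume no Delayed losses and so overstate the bias if both arms lose children. If no child is withdrawn by the team, which the plan regards as likely, there is none. The direction, towards ASSIST, depends on less compliant children gaining less, which is plausible but undocumented. The calculation is for a standardised change score; it was not repeated for each secondary endpoint. This is a worthwhile low-cost improvement, not a flaw that invalidates Study 1.

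**What to change.** 1. In Section 7.2.1, extend the post-testing request of Section 5.5.2 to every reason for leaving, including team-initiated withdrawal. The scheduled T2 and T3 assessments (Target Repetition Task, TOCS+, ICS, FOCUS-34) are then still sought unless permission is withdrawn or attendance is not possible.
2. In Section 9.3 and the SAP, state that Study 1 analyses every randomised child with T1 and T2 data in the randomised arm, whatever amount of ASSIST was received.
3. Report withdrawals by arm and reason, with timing relative to T2.

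The grounds for stopping ASSIST or for withdrawal need no change.

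The cost is a few sentences in the protocol and SAP. The visits are already in the Schedule of Activities, and reasons for withdrawal are already recorded on the case report form. The downside is that scores from children who received little treatment dilute the estimate slightly.

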Lack of efficacy: Given that this study represents a Phase 1 initial efficacy study for a novel treatment with a no-treatment comparator, no efficacy guidelines are available to determine a stopping criterion based on lack of efficacy. In addition, data analysis (blinded speech accuracy judgments and intelligibility) will only be completed after conclusion of each summer camp. As such, stopping each study for lack of efficacy before concluding the summer camp is not possible. However, analysis of Study 1 will inform optimal treatment targets for Study 2, and analysis of Study 2 will inform targets for Study 3, in order to minimize the potential risk of lack of efficacy (e.g., if complex targets lead to larger gains in Study 1 with real word targets, then Study 2 will compare complex words with complex nonwords).

7.3 LOST TO FOLLOW-UP

A child will be considered lost to follow-up if he or she fails to return for T2 or T3 data collection visits and study staff are unable to contact the family after at least 3 attempts (phone and e-mail). Attempts at contact will be documented in the participant file.

8 STUDY ASSESSMENTS AND PROCEDURES

8.1 ENDPOINT AND OTHER NON-SAFETY ASSESSMENTS

Children with CAS complete screening procedures, intervention procedures, and data collection procedures. See **Section 6.1, Study Intervention and Experimental Manipulations Administration** and Clinician Manual for description of intervention procedures. Intervention is administered by SLP graduate students under supervision of a certified, licensed, and experienced SLP.

8.1.1 SCREENING

Children complete tests and procedures to rule out concomitant impairments and to adequately describe their profile of speech, language, and cognitive skills. Responses are recorded on score forms, and any task that requires the child to produce a verbal response is audio and/or video recorded for data analysis and reliability assessment. These tests and procedures are administered within 3 months prior to camp start by SLP graduate students supervised by certified, licensed, and experienced SLPs.

Screening includes the following:

- (1) Pure-Tone Hearing Screening at 0.5, 1, 2, and 4 kHz (ASHA, 1997), to ensure adequate hearing. This involves wearing headphones and responding to tones by raising a hand.
- (2) Dynamic Evaluation of Motor Speech Skill (DEMSS; Strand & McCauley, 2019), a dynamic assessment protocol in which a child's ability to produce certain sounds and sound sequences consistently correctly is assessed with different levels of support (e.g., with visual or tactile cues).
- (3) Diagnostic Evaluation of Articulation and Phonology (DEAP; Dodd et al., 2006) and/or Goldman-Fristoe Test of Articulation (GFTA; Goldman & Fristoe, 2015), to determine presence & severity of speech disorder. These tests involve naming pictures of familiar items and retelling a story or repeating sentences; they sample English consonants in all word positions.
- (4) Oral Mechanism Examination (OME; Robbins & Klee, 1987), to evaluate oral structure and function. This involves tasks such as opening the mouth and sticking out the tongue, or blowing bubbles through a straw.
- (5) Maximum Performance Tasks (Thoonen et al., 1999), to evaluate speech motor capabilities and identify specific types of motor speech disorders in children. This test includes tasks such as saying 'ah' or 'sss' as long as possible, or repeatedly saying 'pataka' as fast as possible.
- (6) Clinical Evaluation of Language Fundamentals (CELF; Semel et al., 2004), to evaluate language skills. This test includes tasks such as finishing sentences after the examiner, repeating sentences, and pointing to pictures in response to examiner's prompts.

- (7) Peabody Picture Vocabulary Test (PPVT; Dunn & Dunn, 2007), to evaluate receptive vocabulary. This test asks children to point to a color picture (out of an array of four pictures) that matches the examiner's spoken word.
- (8) Expressive Vocabulary Test (EVT; Williams, 2007), to evaluate expressive vocabulary. This test asks children to provide one-word responses to a question about a color picture (e.g., What do you call this animal? "A dog").
- (9) The Phonological Awareness subtests of the Comprehensive Test of Phonological Processing (CTOPP; Wagner et al., 1999), to evaluate phonological awareness skills. This test involves tasks such as identifying which two of three pictures (with spoken word) start or end with the same sound.
- (10) The nonverbal subtests of the Reynolds Intellectual Assessment Scales (RIAS; Reynolds & Kamphaus, 2003), to evaluate nonverbal cognitive skills. This test involves tasks such as identifying the 'odd-item-out' in a picture array, without requiring a verbal response.
- (11) The Diagnostic Evaluation of Articulation and Phonology (Dodd, Hua, Crosbie, Holm, & Ozanne, 2006) to evaluate consistency of speech errors. This test asks children to name a set of pictures several times, in random order, so that consistency of errors can be evaluated.
- (12) A single-word naming task involving 50 multisyllabic words to evaluate syllable sequencing and lexical stress. In this non-standardized test, children name pictures or repeat multisyllabic words (e.g., elephant, helicopter). A similar test has been used previously with children as young as 4 years 0 months (Gozzard et al., 2008).
- (13) The Syllable Repetition Task (SRT; Shriberg et al., 2012; Shriberg & Lohmeier, 2008) to evaluate children's ability to repeat progressively longer sequences of simple syllables. This task is implemented on a computer in PowerPoint, with pre-recorded models. The items include the following: bada, dama, bama, mada, naba, daba, nada, maba, bamana, dabama, madaba, nabada, banada, manaba, bamadana, danabama, manabada, nadamaba.
- (14) A connected speech sample will also be collected to characterize the nature and consistency of speech errors and prosody. Connected speech samples may involve free conversation and/or based on picture description (for example the Park Play scene; Patel & Connaghan, 2014).

Parents also complete the following:

- Contact information form (address, preferred contact method, and emergency contact).
- Background questionnaire about developmental milestones, language background, and other information relevant to understanding the child's speech and language profile and context. This questionnaire is administered at the first visit during the pre-camp period.
- Functional communication questionnaire (Wilson & [name], 2014) to solicit a list of potential treatment targets based on personal interests and needs. Together with parent and child, the research team reviews for completeness and clarity and to prioritize possible targets for inclusion in treatment. This questionnaire is administered during the pre-camp period.

Finally, with parents' permission, we also seek further information from existing records elsewhere, which may include speech-language pathology evaluation reports and treatment notes, neurological reports and scans, neuropsychological test results, and Individualized Educational Programs. This information provides further background information that will facilitate interpretation of the findings.

Screening takes place within 3 months of camp start within a recruitment cycle, and involves up to 7 hours of testing divided over 2-7 sessions depending on child stamina and scheduling availability. For diagnosis of CAS, three expert SLPs (Co-I [name] and the two Key Consultants [name] and [name]) each provide an independent rating based on live or video-recorded sessions. Video recordings are shared with Key Consultants via TU SafeSend, a secure file sharing system hosted by Temple University. Rating for presence of CAS uses the CAS3SLP scale, which includes 3 options: 0 = no CAS, 1 = possible CAS, 2 = CAS. To meet inclusion criterion 5a (clinical judgment of presence of CAS; see **Section 5.1, Inclusion Criteria**), children must receive a mean CAS3SLP score (across the three expert SLPs) > 1. Expert SLPs share their rating with the PI, who aggregates the ratings to determine eligibility.

